6.4.1.1.1 Serious Adverse Events

An SAE is defined as any event that

- results in death
- is immediately life threatening
- requires inpatient hospitalisation or prolongation of existing hospitalisation
- results in persistent or significant disability/incapacity
- is a congenital anomaly/birth defect

Important medical events that may not result in death, be life threatening, or require hospitalisation may be considered SAEs when, based upon appropriate medical judgment, they may jeopardise the participant or may require medical or surgical intervention to prevent one of the outcomes listed in this definition. Examples of such medical events include allergic bronchospasm requiring intensive treatment in an emergency room or at home, blood dyscrasias or convulsions that do not result in inpatient hospitalisation, or the development of drug dependency or drug abuse.

6.4.1.1.2 Local and General Systemic Reactogenicity Symptoms

Solicited AEs (e.g., local and general systemic reactogenicity symptoms) will be captured in the Safety Subset of approximately 2,000 participants and in the seasonal influenza vaccine co-administration sub-study of approximately 400 participants. Participants will record all local reactogenicity symptoms for each injection of study vaccine at each location (ideally in opposite deltoids) while recording of general systemic reactogenicity symptoms may not be assigned to either injection site. Local reactogenicity symptoms should not be recorded for the influenza vaccine injection site. Solicited AEs, collected through an electronic diary (e-Diary), will be recorded from the time of study vaccination until 7 days after study vaccination.

Site-specific local (arm) and general systemic reactogenicity reactions including start and stop dates will be recorded and the investigator will apply a standard toxicology grading at the subsequent study visit (Section 9.4, Appendix 3). Should any reactogenicity event extend beyond 7 days after study vaccination and be clinically significant by toxicity grade 1 or greater, then it will be recorded as an unsolicited AE with a start date on the 8th day following study vaccination and followed to resolution.

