1.3 Clinical Experience

The first clinical study with SARS-CoV-2 rS nanoparticle vaccine is 2019nCoV-101, which is a 2-part, randomised, observer-blinded, placebo-controlled, Phase 1/2 trial. Part 1 (Phase 1) is designed to evaluate the immunogenicity and safety of SARS-CoV-2 rS nanoparticle vaccine with or without Matrix-M1 adjuvant in 131 healthy participants \geq 18 to \leq 59 years of age. Results of an interim analysis at Day 35 showed that SARS-CoV-2 rS with Matrix-M1 adjuvant was well tolerated and elicited robust immune responses [Keech 2020]. There were no serious adverse events (SAEs) or adverse events of special interest (AESIs). Reactogenicity was mainly mild in severity and of short duration (mean \leq 2 days), with second vaccinations inducing greater local and systemic reactogenicity. The adjuvant significantly enhanced immune responses (anti-S IgG, hACE2 receptor binding inhibition antibody, and neutralising antibody) and was antigen dose-sparing, and the 2 dose 5µg SARS-CoV-2 rS/Matrix-M1 adjuvant induced mean anti-S IgG and neutralising antibody responses that exceeded the mean responses in convalescent sera from COVID-19 patients with clinically significant illnesses. The vaccine also induced antigen-specific T cells with a largely Th1 phenotype.

Part 2 (Phase 2) is designed to evaluate the immunogenicity, safety, and preliminary efficacy of SARS-CoV-2 rS and Matrix-M1 adjuvant in up to 1,500 healthy adults \geq 18 to \leq 84 years of age with more co-morbidities than the participant population in Part 1 of the study.

Novavax has, in its internally-sponsored clinical trials, tested baculovirus-Sf9-produced nanoparticle vaccines in 14,848 participants comprising older adults, young adults, and a limited number of children 2 to 5 years of age; and also including 3,075 pregnant women,

with acceptable safety. Matrix-M adjuvant has been given to 4,311 humans (of which, approximately 2,657 humans received nanoparticle vaccine) with acceptable short-term reactogenicity, and an unremarkable long-term safety profile.

Further details on the clinical experience of the study vaccine can be found in the SARS-CoV-2 rS IB.

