The study will consist of the screening period (Days -30 to 0); study vaccination Days 0 and 21 (+7-day window); and outpatient study visits on Day 0, Day 21 (+ 7 days), and Day 35 (14 days minimum after second study vaccination [+ 7 days]); and at 3, 6, and 12 months (\pm 15 days) after last study vaccination.

The duration of individual participation, including screening, will be a maximum of 1 year after second study vaccination (Day 386 ± 15 days). This will be an event-driven study for the assessment of vaccine efficacy (VE) and will end when a sufficient number of events

have been observed, yet all participants will be followed for the entire study duration for safety endpoints.

A licensed seasonal influenza co-administration sub-study will be conducted in the first 400 participants who meet the additional inclusion criteria for this study. Participants may be enrolled at selected study sites due to the availability of seasonal influenza vaccine. After being randomised to receive IM injections of SARS-CoV-2 rS with Matrix-M1 adjuvant or placebo, sub-study participants will receive a licensed seasonal influenza vaccine on Day 0 in the opposite deltoid. These participants will be part of the solicited AE safety subset analysis.

Given that this study and others will enrol during the influenza virus season and that the highest at-risk population, namely the elderly and adults with comorbid conditions for influenza mirrors that of SARS-CoV-2, a co-vaccination sub-study is included. This sub-group will undergo the same safety and efficacy evaluations as the entire study population. In addition, the entire sub-study will have reactogenicity assessed. This group must not have had a current season licensed influenza vaccine and have no prior history of allergy or severe reaction to seasonal influenza vaccine. To assess the possible impact of the study vaccine on the immunogenicity of the influenza vaccine, this group will also have a hemagglutination inhibition assay (HAI) performed.

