3.1 Study Vaccination Pause Rules

Study vaccination pause rules based on reactogenicity, AEs, and SAEs related to study participation will be in place to monitor participant safety during the study.

AEs meeting any one of the following criteria will result in a hold being placed on subsequent study vaccinations pending further review by the SMC at the direction of the SMC chair:

• Any toxicity grade 3 or higher (severe or potentially life-threatening) solicited (local or systemic) single AE term occurring in ≥ 10% of participants (after a minimum of 100 subjects are enroled) in the SARS-CoV-2 rS with Matrix-M1 adjuvant group within the first 7 days after study vaccination.

• Any severe unsolicited single AE preferred term for which the investigator assesses as related that occurs in ≥ 5% of participants (after a minimum of 100 subjects are enroled) in the SARS-CoV-2 rS with Matrix-M1 adjuvant group, within the first 7 days after study vaccination.

In addition, any SAE assessed as related to vaccine (final assessment by the sponsor) will be reported by the sponsor to the SMC Chair as soon as possible, and within 24 hours of the sponsor's awareness of the event. Based on this initial report of the event to the SMC Chair, the Chair may advise the sponsor to immediately pause enrolment and further dosing in either some or all subjects in the study and to convene an ad hoc meeting, or make alternative recommendations. The SMC Charter defines processes for how this review will occur and how the Chair's recommendations will be documented.

The sponsor, along with medical monitor, may request an SMC review for any safety concerns that may arise in the study, even if they are not associated with any specific pause rule; for example, any SAE for which causality is at least possibly related.

The 400 subject influenza vaccine co-administration study will utilize the same pause rules with one difference due to the expectation of greater reactogenicity and the small size:

Any grade 3 or higher (severe or potentially life-threatening) solicited (local or systemic) single AE term occurring in ≥ 20% of participants in the SARS-CoV-2 rS with Matrix-M1 adjuvant plus seasonal influenza vaccine group, within the first 7 days after study vaccination.

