4.4 Withdrawal of Participants from the Study

4.4.1 Reasons for Withdrawal

Participants can withdraw consent and discontinue from the study at any time, for any reason. Participants may refuse further procedures (including study vaccination) but are encouraged to remain in the study for safety follow-up. In such cases where only safety is being conducted, participant contact could be managed via telemedicine contact (e.g., telephone, web chat, video, FaceTime).

The investigator will **withhold** further study vaccination from a participant in the study if the participant:

- 1. Is noncompliant with the protocol.
- 2. Experiences an SAE or intolerable AE(s) for which study vaccination is not advised by the investigator.
- 3. Becomes pregnant (discontinuation of further study vaccination required).

The investigator can also withdraw a participant upon the request of the sponsor or if the sponsor terminates the study.

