6.1.3 Day 21 – Second Study Vaccination (+ 7 days)

- Prior and concomitant medications. Concomitant medications include all medications (including vaccines) taken by the participant.
- Urine pregnancy test for women of childbearing potential only. A urine pregnancy test will be performed prior to each study vaccination. A positive urine pregnancy test at any time will result in the participant not receiving any further study vaccination.
- Symptom-directed (targeted) physical examination, including lymphatic assessment of injected upper extremity. Physical examination must be done prior to study vaccination.
- Blood sampling for HAI for participants who received licensed seasonal influenza vaccine on Day 0 in the approximately 400 participants in the licensed seasonal influenza co-administration sub-study.
- Nose/throat samples will be collected to test for SARS-CoV-2 (PCR) only if the participant has any COVID-19 symptoms or significant exposure history between Days 0 and 21. Results of that test are not required for study vaccination, but participants who are symptomatic may be have second study vaccination delayed per protocol. Participants found to be SARS-CoV-2 positive on Day 21 will be excluded from the immunogenicity analyses of the study as per the SAP.
- Pre-injection vital sign collection (respiratory rate, blood pressure, pulse rate, pulse oximetry, and oral temperature [or via forehead/ear reader]) before study vaccination to ensure participant has no evidence of fever prior to study vaccination.
- Alcohol swab cleansing of the injection site for study vaccine (SARS-CoV-2 rS with Matrix-M1 adjuvant or placebo).
- Vaccination of study vaccine as an IM injection into the opposite deltoid muscle of the Day 0 study vaccine.
- Monitoring for reactogenicity, participants will remain in clinic for at least 30 minutes to be monitored for any severe reactogenicity. Severe reactions will be noted as AEs on day of study vaccination.
- Post-injection vital sign collection (respiratory rate, blood pressure, pulse rate, pulse oximetry, and oral temperature [or via forehead/ear reader]) at approximately 15 to 30 minutes after study vaccination to check for any reactions to the study vaccine.

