6.4 Safety Assessments

The timing and frequency of all safety assessments are listed in the SOE (Table 3-1).

After each study vaccination, including the licensed seasonal influenza vaccine for participants in the seasonal influenza vaccine co-administration sub-study, participants will remain under observation at the study site for at least 30 minutes for the presence of any acute reactions and solicited AEs. Solicited AEs, collected through an electronic diary (e-Diary), will be recorded at each study vaccination visit from the time of study vaccination until 7 days after study vaccination in all participants in the seasonal influenza vaccine co-administration sub-study and a subgroup of all other participants. Participants in the licensed seasonal influenza vaccine co-administration sub-study will record local reactogenicity for the study vaccine injection site only.

All participants will be assessed for unsolicited AEs from the time of first study vacation until Day 49; SAEs will be assessed from the time the informed consent is signed until completion of the participant's last study-related procedure; all MAAEs will be reported from the time of first study vaccination until Day 35; MAAEs related to study vaccination and AESIs will be reported from the time of first study vaccination until completion of the participant's last study-related procedure. All AEs will be followed until resolution or until clinically stable.

Safety assessments will include monitoring and recording of solicited (local and systemic reactogenicity events) and unsolicited AEs; MAAEs; AESI; SAEs; vital sign measurements on day of study vaccinations; and physical examination findings. COVID-19 severity will be categorised as virologically confirmed, mild, moderate, or severe according to protocol-specified criteria (Table 2-1). Recording of solicited and unsolicited AEs may be conducted by electronic data capture (EDC)/reporting. PIMMCs and AESIs specific to potential disease

enhancement for COVID-19 will also be monitored (see Section 9.5 [Appendix 4] for details).

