6.4.4 Safety Monitoring

Safety oversight will be conducted by an SMC during the course of the study. The SMC is an independent group of experts that monitors participant safety and advises the sponsor. The SMC members will be separate and independent of site personnel participating in this study and should not have a scientific, financial, or other conflict of interest related to this study or the sponsor. The SMC will consist of members with appropriate expertise to contribute to the interpretation of the data from this study.

A global SMC was convened to oversee the safety of the ongoing Phase 1/2 study (Protocol 2019nCoV-101) and will oversee 1 or more additional studies across the SARS-CoV-2 rS vaccine program. A separate SMC will be convened for this study. The designated SMC will monitor the safety of participants in the study and will follow an SMC charter. The SMC will review blinded and unblinded safety and reactogenicity data. The SMC will also review sufficient clinical event data to ensure detection of evidence of enhanced disease. The SMC will convene to perform safety reviews on a scheduled basis as per the SMC charter; for immediate concerns regarding safety observations during this study; and as needed.

The SMC will operate under the rules of a sponsor-approved charter that will be approved at the organisational meeting of the SMC. At this time, each data element that the SMC needs to assess will be clearly defined. Procedures for SMC reviews/meetings will be defined in the charter. The SMC will review applicable data for safety assessments (AEs by classifications) and any clinical data that may be of significance to this review (e.g., demographics, study vaccination timing, and medications). Additional data may be requested by the SMC, and interim statistical reports may be generated as deemed necessary and appropriate for this review. The SMC may receive data in aggregate and presented by study vaccine group. The SMC may also be provided with expected and observed rates of the expected AEs in an unblinded fashion and may request the study vaccine assignment be unblinded for an individual participant if required for safety assessment.

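### The main-study pause rule for grade 3 solicited reactions is not tied to the participants who keep a diary, and the protocol does not say which toxicity grade feeds it

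*Protocol*

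**What the plan says.** Section 3.1 (repeated in the Synopsis) places a hold on further study vaccination when a single solicited term of toxicity grade 3 or higher occurs within 7 days of a dose, "occurring in ≥ 10% of participants (after a minimum of 100 subjects are enroled) in the SARS-CoV-2 rS with Matrix-M1 adjuvant group". The next rule, for severe related unsolicited events at 5%, uses the same population wording. The influenza sub-study replaces the 10% with 20% of its own vaccine group.

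The two kinds of event are not collected in the same people. Unsolicited events come from everyone: "All participants will be assessed for unsolicited AEs from the time of first study vacation until Day 49". Solicited events are captured by e-Diary for 7 days after each dose, only in a Safety Subset of about 2,000 and in the sub-study of about 400 (Sections 6.4.1.1.2 and 7.3.3).

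For diary reactions, Section 6.4.1.1.2 says that "the investigator will apply a standard toxicology grading at the subsequent study visit (Section 9.4, Appendix 3"). The next scheduled visit after dose 1 is Day 21 (+7 days), where dose 2 is given: "Vaccination of study vaccine as an IM injection into the opposite deltoid muscle of the Day 0 study vaccine" (Section 6.1.3). After dose 2 it is "Day 35 (14 days minimum after second study vaccination [+ 7 days"]) (Section 3). Section 6.4.4 gives the safety monitoring committee (SMC) reactogenicity data and leaves the content of its reviews to a charter, approved at a meeting where "each data element that the SMC needs to assess will be clearly defined".

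**The concern.** A stopping percentage means something only if its numerator and denominator come from the same people. Here only diary keepers can contribute solicited events, while the stated denominator is the vaccine group. If the words are applied as they stand, the rule becomes less sensitive as enrolment goes on, and by full enrolment it is out of reach at any plausible grade 3 rate.

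The timing issue is separate and affects both solicited rules. The rule exists to hold further doses. If the visit grade is its input, information on dose 1 arrives only as second doses fall due, and Section 1.3 summarises Phase 1 "with second vaccinations inducing greater local and systemic reactogenicity", although reactions were mainly mild and short.

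What is at stake is the detection of common, mostly non-serious grade 3 reactogenicity in aggregate. The efficacy result is not affected.

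**Working it through.** The protocol gives no trigger probability, diary share or lag for these rules, so there is no planned figure to reproduce.

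**Inputs.** 15,000 participants randomised 1:1, so 7,500 vaccinees (Section 7.1). Safety Subset about 2,000 and sub-study about 400 (Section 6.4.1.1.2). Diary period 7 days. Next visits: Day 21-28 after dose 1, and 14-21 days after dose 2. Assumption: the 1:1 split also holds within the subsets.

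**Share of main-study vaccinees with a diary.** Sub-study vaccinees are 400/2 = 200, so main-study vaccinees are 7,500 - 200 = 7,300. The text does not settle whether the 400 lie inside the 2,000.
- 400 outside the 2,000: 2,000/2 = 1,000 diary vaccinees; 1,000/7,300 = 13.7%.
- 400 inside: (2,000 - 400)/2 = 800; 800/7,300 = 11.0%.

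**Literal rule at full enrolment.** Events needed: 0.10 × 7,300 = 730. As a share of diary keepers: 730/1,000 = 73%, or 730/800 = 91%. A true 20% grade 3 rate gives 0.20 × 800 to 0.20 × 1,000 = 160-200 events, or 160/7,300 to 200/7,300 = 2.2-2.7%. That is no hold. Tied to diary keepers, the rule needs 80-100 events, and 160-200 exceed it clearly.

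**Dependence on enrolment order.** If diary participants are spread evenly over accrual, the literal rule needs 73-91% throughout. If they all enrol first, the two readings agree until the subset fills, and then diverge:

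| Main-study vaccinees | Events needed | Share of 1,000 / 800 diary keepers |
|---|---|---|
| 2,500 | 250 | 25% / 31% |
| 5,000 | 500 | 50% / 62.5% |
| 7,300 | 730 | 73% / 91% |

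In the enrol-first case a true 20% rate still meets the literal rule while there are at most 160/0.10 = 1,600 to 200/0.10 = 2,000 main-study vaccinees.

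**How the rule behaves with a diary denominator.** Exact binomial chance of 10 or more events among 100 diary vaccinees, one term, one look:

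| True grade 3 rate | P(hold) |
|---|---|
| 5% | 2.8% |
| 8% | 27.8% |
| 10% | 54.9% |
| 15% | 94.5% |
| 20% | 99.8% |

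The threshold is sensible once its population is right. Repeated looks raise the chance of a hold at rates just below it. In a simulation at a true 8% rate, with looks every 25-50 diary vaccinees from 100 up to 800-1,000 (spacing assumed), the chance for one term is about 40-41%. At 5% it stays near 3%.

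**Lag from diary close to the visit grade.**
- Dose 1: 21 - 7 = 14 to 28 - 7 = 21 days.
- Dose 2: 14 - 7 = 7 to 21 - 7 = 14 days.

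Doses given during the lag are not estimated, because the accrual rate is not stated.

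**The case against.** Solicited events exist only where they are solicited, so a competent safety team would probably divide by diary keepers. Section 7.3.3 also promises percentages by vaccine group without naming a denominator, and nobody would divide by 7,500 there. This stands as a reason to treat the denominator as faulty wording. A reader might infer that the rule will be run over the whole arm and is therefore inoperative. The documents do not show that. But the rule is a hold criterion and should not depend on the reader's correction, particularly when the adjacent rule uses the same words for events collected in everyone.

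On timing, a reader might infer that the rules require the visit grade, so that no hold can come before second doses begin. The text does not support that either. Section 3.1 names no assessor for the solicited grade, the diary is electronic, several Table 9-1 criteria (temperature, diameter) could be read from entries directly, and the charter may arrange this. What stands is that the visit grading is the only such step the protocol states.

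Other safeguards exist. Related SAEs reach the SMC Chair within 24 hours, the sponsor may request SMC review for any safety concern, Table 3-1 schedules an eligibility check before the Day 21 dose, and the investigator withholds further vaccination when a participant "Experiences an SAE or intolerable AE(s) for which study vaccination is not advised by the investigator". These protect individuals or rest on judgement; none is stated to apply the 10% or 20% rule.

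**Conclusion.** The denominator point holds. As worded, the main-study solicited rule is not limited to the 11-14% of main-study vaccinees whose solicited reactions are captured, and at full enrolment it could not fire at a true 20% grade 3 rate. This rests on a 1:1 split within the subsets and on the literal reading. The size of the divergence earlier in accrual depends on when diary participants enrol. The influenza 20% rule has no denominator problem, because that whole group keeps a diary.

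The timing point holds as a secondary gap affecting both solicited rules: the protocol does not say which grade feeds them, and the one grading step it states comes 14-21 days after the dose 1 diary closes. The unseen charter may already close this gap, but not the wording of the denominator in Section 3.1.

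Severity is minor to moderate. The gap concerns aggregate, mostly non-serious grade 3 reactogenicity. The unsolicited-event rule, related-SAE reporting and individual withholding of doses are unaffected.

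**What to change.** (a) In Section 3.1 and the Synopsis, define both the denominator and the minimum of 100 for the main-study solicited rule as dosed vaccine-group participants assigned to the e-Diary, outside the influenza sub-study.

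(b) In Section 3.1, state that for both solicited rules provisional Table 9-1 grades are derived from diary entries as they arrive, wherever the diary captures the criterion, with investigator confirmation at the visit. If the charter already says this, a cross-reference is enough. The frequency of counting can stay with the charter. The 10% and 20% thresholds do not change.

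The cost is protocol wording, a grade derivation and an unblinded count by group. The diary fields are not shown; a criterion the diary does not capture, such as narcotic use, needs an added field or waits for the investigator. Some holds will rest on provisional grades later revised, and at true rates just under 10% a hold is fairly likely (about 28% for one term at 8% at the first look at 100, more with further looks or several terms). Each such hold leads to SMC review, not to stopping the trial.
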